12. PLANS FOR DISSEMINATING AND COMMUNATING STUDY RESULTS

This database analysis will be performed by the Bordeaux Pharmacoépi, INSERM CIC1401, an academic research organization (ARO), for which scientific communication and publication is a major component of its activities. Study methods and results will be submitted to scientific meetings and for publication in international scientific journals.

ANNEX 1. LIST OF STAND-ALONE DOCUMENTS

Number	Title
1	List of ICD-10 codes for bleeding

ANNEX 2. ENCePP CHECKLIST FOR STUDY PROTOCOLS

A copy of the ENCePP Checklist for Study protocols available at website encepp.eu/standards_and_guidances completed and signed by the main author of the study protocol is included in ANNEX 2.

ANNEX 3. ADDITIONAL INFORMATION

None.

ANNEX 4. SIGNATURE PAGES

ANNEX 1: LIST OF STAND-ALONE DOCUMENTS

Number 1: List of ICD-10 codes for bleeding leading to an hospitalization

- 1) All ICD codes with the following label were selected: "hémorragie (hemorrhage), hémorragique (hemorrhagic), saignement (bleeding), épistaxis (epistaxis), otorragie (otorrhagia), hématomèse (hematemesis), rectorragie (proctorrhagia), melena (melena), hématurie (hematuria), hémoptysie (hemoptysis), métrorragies (metrorrhagia), hémopéritoine (hemoperitonea), hémothorax (hemothorax), hémopéricarde (hemopericardia)".
- 2) ICD label that do not correspond to a bleeding event were excluded (grey list), such as:
 - No bleeding
 - Chronic disease with bleeding in the definition
 - Infectious diseases with bleeding in the definition
 - Aftereffect of cerebral haemorrhage
 - Accident during surgical and medical care, including other events than a bleeding.
- 3) ICD code for bleeding during abortion or delivery are also excluded (grey list):

ICD-10 code	ICD label (French)	ICD label (English)	Key word
Selected Codes			
D62	Anémie posthémorragique aiguë	Acute posthaemorrhagic anaemia	Hémorragique
D683	Troubles hémorragiques dus à des anticoagulants circulants	Haemorrhagic disorder due to circulating anticoagulants	Hémorragique
D698	Autres affections hémorragiques précisées	Other specified haemorrhagic conditions	Hémorragique
D699	Affection hémorragique, sans précision	Haemorrhagic condition, unspecified	Hémorragique
H113	Hémorragie conjonctivale	Conjunctival haemorrhage	Hémorragie
H313	Hémorragie et rupture de la choroïde	Choroidal haemorrhage and rupture	Hémorragie
H356	Hémorragie rétinienne	Retinal haemorrhage	Hémorragie
H431	Hémorragie du corps vitré	Vitreous haemorrhage	Hémorragie
H450	Hémorragie du corps vitré au cours de maladies classées ailleurs	Vitreous haemorrhage in diseases classified elsewhere	Hémorragie
H922	Otorragie	Otorrhagia	Otorragie
I230	Hémopéricarde comme complication récente d'un infarctus aigu du myocarde	Haemopericardium as current complication following acute myocardial infarction	Hémopéricarde
I312	Hémopéricarde, non classé ailleurs	Haemopericardium, not elsewhere classified	Hémopéricarde
I600	Hémorragie sous-arachnoïdienne de la bifurcation et du siphon carotidien	Subarachnoid haemorrhage from carotid siphon and bifurcation	Hémorragie
I601	Hémorragie sous-arachnoïdienne de l'artère cérébrale moyenne	Subarachnoid haemorrhage from middle cerebral artery	Hémorragie

I602	Hémorragie sous-arachnoïdienne de l'artère communicante antérieure	Subarachnoid haemorrhage from anterior communicating artery	Hémorragie
I603	Hémorragie sous-arachnoïdienne de l'artère communicante postérieure	Subarachnoid haemorrhage from posterior communicating artery	Hémorragie
I604	Hémorragie sous-arachnoïdienne de l'artère basilaire	Subarachnoid haemorrhage from basilar artery	Hémorragie
I605	Hémorragie sous-arachnoïdienne de l'artère vertébrale	Subarachnoid haemorrhage from vertebral artery	Hémorragie
I606	Hémorragie sous-arachnoïdienne d'autres artères intracrâniennes	Subarachnoid haemorrhage from other intracranial arteries	Hémorragie
I607	Hémorragie sous-arachnoïdienne d'une artère intracrânienne, sans précision	Subarachnoid haemorrhage from intracranial artery, unspecified	Hémorragie
I608	Autres hémorragies sous-arachnoïdiennes	Other subarachnoid haemorrhage	Hémorragie
I609	Hémorragie sous-arachnoïdienne, sans précision	Subarachnoid haemorrhage, unspecified	Hémorragie
I610	Hémorragie intracérébrale hémisphérique, sous-corticale	Intracerebral haemorrhage in hemisphere, subcortical	Hémorragie
I611	Hémorragie intracérébrale hémisphérique, corticale	Intracerebral haemorrhage in hemisphere, cortical	Hémorragie
I612	Hémorragie intracérébrale hémisphérique, non précisée	Intracerebral haemorrhage in hemisphere, unspecified	Hémorragie
I613	Hémorragie intracérébrale du tronc cérébral	Intracerebral haemorrhage in brain stem	Hémorragie
I614	Hémorragie intracérébrale cérébelleuse	Intracerebral haemorrhage in cerebellum	Hémorragie
I615	Hémorragie intracérébrale intraventriculaire	Intracerebral haemorrhage, intraventricular	Hémorragie
I616	Hémorragie intracérébrale, localisations multiples	Intracerebral haemorrhage, multiple localized	Hémorragie
I618	Autres hémorragies intracérébrales	Other intracerebral haemorrhage	Hémorragie
I619	Hémorragie intracérébrale, sans précision	Intracerebral haemorrhage, unspecified	Hémorragie
I620	Hémorragie sous-durale (aiguë) (non traumatique)	Subdural haemorrhage (acute)(nontraumatic)	Hémorragie
I621	Hémorragie extradurale non traumatique	Nontraumatic extradural haemorrhage	Hémorragie
I629	Hémorragie intracrânienne (non traumatique), sans précision	Intracranial haemorrhage (nontraumatic), unspecified	Hémorragie
I850	Varices œsophagiennes hémorragiques	Oesophageal varices with bleeding	Hémorragique
I983	Varices œsophagiennes hémorragiques au cours de maladies classées ailleurs	Oesophageal varices with bleeding in diseases classified elsewhere	Hémorragique
J942	Hémothorax	Haemothorax	Hémothorax
K226	Syndrome de dilacération hémorragique gastro-œsophagienne	Gastro-oesophageal laceration-haemorrhage syndrome	Hémorragique
K250	Ulcère de l'estomac aigu, avec hémorragie	Gastric ulcer: Acute with haemorrhage	Hémorragie
K252	Ulcère de l'estomac aigu, avec hémorragie et perforation	Gastric ulcer: Acute with both haemorrhage and perforation	Hémorragie
K254	Ulcère de l'estomac chronique ou non précisé, avec hémorragie	Gastric ulcer: Chronic or unspecified with haemorrhage	Hémorragie
K256	Ulcère de l'estomac chronique ou non précisé, avec hémorragie et perforation	Gastric ulcer: Chronic or unspecified with both haemorrhage and perforation	Hémorragie
K260	Ulcère du duodénum aigu, avec hémorragie	Duodenal ulcer: Acute with haemorrhage	Hémorragie
K262	Ulcère du duodénum aigu, avec hémorragie et perforation	Duodenal ulcer: Acute with both haemorrhage and perforation	Hémorragie

K264	Ulcère du duodénum chronique ou non précisé, avec hémorragie	Duodenal ulcer: Chronic or unspecified with haemorrhage	Hémorragie
K266	Ulcère du duodénum chronique ou non précisé, avec hémorragie et perforation	Duodenal ulcer: Chronic or unspecified with both haemorrhage and perforation	Hémorragie
K270	Ulcère digestif, de siège non précisé, aigu avec hémorragie	Peptic ulcer, site unspecified: Acute with haemorrhage	Hémorragie
K272	Ulcère digestif, de siège non précisé, aigu avec hémorragie et perforation	Peptic ulcer, site unspecified: Acute with both haemorrhage and perforation	Hémorragie
K274	Ulcère digestif, de siège non précisé, chronique ou non précisé, avec hémorragie	Peptic ulcer, site unspecified: Chronic or unspecified with haemorrhage	Hémorragie
K276	Ulcère digestif, de siège non précisé, chronique ou non précisé, avec hémorragie et perforation	Peptic ulcer, site unspecified: Chronic or unspecified with both haemorrhage and perforation	Hémorragie
K280	Ulcère gastro-jéjunal aigu, avec hémorragie	Gastrojejunal ulcer: Acute with haemorrhage	Hémorragie
K282	Ulcère gastro-jéjunal aigu, avec hémorragie et perforation	Gastrojejunal ulcer: Acute with both haemorrhage and perforation	Hémorragie
K284	Ulcère gastro-jéjunal chronique ou non précisé, avec hémorragie	Gastrojejunal ulcer: Chronic or unspecified with haemorrhage	Hémorragie
K286	Ulcère gastro-jéjunal chronique ou non précisé, avec hémorragie et perforation	Gastrojejunal ulcer: Chronic or unspecified with both haemorrhage and perforation	Hémorragie
K290	Gastrite hémorragique aiguë	Acute haemorrhagic gastritis	Hémorragique
K625	Hémorragie de l'anus et du rectum	Haemorrhage of anus and rectum	Hémorragie
K661	Hémopéritoine	Haemoperitoneum	Hémopéritoine
K762	Nécrose hémorragique centrale du foie	Central haemorrhagic necrosis of liver	Hémorragique
K920	Hématémèse	Haematemesis	Hématémèse
K921	Mélæna	Melaena	mélaena
K922	Hémorragie gastro-intestinale, sans précision	Gastrointestinal haemorrhage, unspecified	Hémorragie
M250	Hémarthrose	Haemarthrosis	Hémarthrose
N020	Hématurie récidivante et persistante avec anomalies glomérulaires mineures	Recurrent and persistent haematuria: Minor glomerular abnormality	Hématurie
N021	Hématurie récidivante et persistante avec lésions glomérulaires segmentaires et focales	Recurrent and persistent haematuria: Focal and segmental glomerular lesions	Hématurie
N022	Hématurie récidivante et persistante avec glomérulonéphrite membraneuse diffuse	Recurrent and persistent haematuria: Diffuse membranous glomerulonephritis	Hématurie
N023	Hématurie récidivante et persistante avec glomérulonéphrite proliférative mésangiale diffuse	Recurrent and persistent haematuria: Diffuse mesangial proliferative glomerulonephritis	Hématurie
N024	Hématurie récidivante et persistante avec glomérulonéphrite proliférative endocapillaire diffuse	Recurrent and persistent haematuria: Diffuse endocapillary proliferative glomerulonephritis	Hématurie
N025	Hématurie récidivante et persistante avec glomérulonéphrite mésangiocapillaire diffuse	Recurrent and persistent haematuria: Diffuse mesangiocapillary glomerulonephritis	Hématurie
N026	Hématurie récidivante et persistante avec maladie à dépôt dense	Recurrent and persistent haematuria: Dense deposit disease	Hématurie
N027	Hématurie récidivante et persistante avec glomérulonéphrite diffuse en croissant	Recurrent and persistent haematuria: Diffuse crescentic glomerulonephritis	Hématurie
N028	Hématuries récidivantes et persistantes avec autres lésions	Recurrent and persistent haematuria: Other	Hématurie

	morphologiques		
N029	Hématurie récidivante et persistante, sans précision	Recurrent and persistent haematuria: Unspecified	Hématurie
N421	Congestion et hémorragie prostatiques	Congestion and haemorrhage of prostate	Hémorragie
N920	N920 « Menstruation trop abondante et trop fréquente avec cycle menstruel régulier »	Excessive and frequent menstruation with regular cycle	Menstruation trop abondante
N920	N921 « Menstruation trop abondante et trop fréquente avec cycle menstruel irrégulier »	Excessive and frequent menstruation with irregular cycle	Menstruation trop abondante
N923	Saignements de l'ovulation	Ovulation bleeding	Saignement
N924	Saignements abondants de la préménopause	Excessive bleeding in the premenopausal period	Saignement
N930	Saignements post-coïtaux et de contact	Postcoital and contact bleeding	Saignement
N938	Autres saignements anormaux précisés de l'utérus et du vagin	Other specified abnormal uterine and vaginal bleeding	Saignement
N939	Saignement anormal de l'utérus et du vagin, sans précision	Abnormal uterine and vaginal bleeding, unspecified	Saignement
N950	Saignements post-ménopausiques	Postmenopausal bleeding	Saignement
O031	Avortement spontané incomplet, compliqué d'une hémorragie retardée ou sévère	Spontaneous abortion: Incomplete, complicated by delayed or excessive haemorrhage	Hémorragie
O036	Avortement spontané complet ou sans précision, compliqué d'une hémorragie retardée ou sévère	Spontaneous abortion: Complete or unspecified, complicated by delayed or excessive haemorrhage	Hémorragie
O041	Avortement médical incomplet, compliqué d'une hémorragie retardée ou sévère	Medical abortion: Incomplete, complicated by delayed or excessive haemorrhage	Hémorragie
O046	Avortement médical complet ou sans précision, compliqué d'une hémorragie retardée ou sévère	Medical abortion: Complete or unspecified, complicated by delayed or excessive haemorrhage	Hémorragie
O051	Autres formes d'avortement incomplet, compliqué d'une hémorragie retardée ou sévère	Other abortion: Incomplete, complicated by delayed or excessive haemorrhage	Hémorragie
O056	Autres formes d'avortement complet ou sans précision, compliqué d'une hémorragie retardée ou sévère	Other abortion: Complete or unspecified, complicated by delayed or excessive haemorrhage	Hémorragie
O061	Avortement sans précision, incomplet, compliqué d'une hémorragie retardée ou sévère	Unspecified abortion: Incomplete, complicated by delayed or excessive haemorrhage	Hémorragie
O066	Avortement sans précision, complet ou sans précision, compliqué d'une hémorragie retardée ou sévère	Unspecified abortion: Complete or unspecified, complicated by delayed or excessive haemorrhage	Hémorragie
O071	Échec d'une tentative d'avortement médical, compliqué d'une hémorragie retardée ou sévère	Failed medical abortion, complicated by delayed or excessive haemorrhage	Hémorragie
O076	Échec d'une tentative d'avortement, autres et sans précision, compliqués d'une hémorragie retardée ou sévère	Other and unspecified failed attempted abortion, complicated by delayed or excessive haemorrhage	Hémorragie
O081	Hémorragie retardée ou sévère consécutive à un avortement, une grossesse extra-utérine et molaire	Delayed or excessive haemorrhage following abortion and ectopic and molar pregnancy	Hémorragie
O208	Autres hémorragies du début de la grossesse	Other haemorrhage in early pregnancy	Hémorragie
O209	Hémorragie du début de la grossesse, sans précision	Haemorrhage in early pregnancy, unspecified	Hémorragie

O441	Placenta praevia avec hémorragie	Placenta praevia with haemorrhage	Hémorragie
O460	Hémorragie précédant l'accouchement avec anomalie de la coagulation	Antepartum haemorrhage with coagulation defect	Hémorragie
O468	Autres hémorragies précédant l'accouchement	Other antepartum haemorrhage	Hémorragie
O469	Hémorragie précédant l'accouchement, sans précision	Antepartum haemorrhage, unspecified	Hémorragie
O670	Hémorragie pendant l'accouchement avec anomalie de la coagulation	Intrapartum haemorrhage with coagulation defect	Hémorragie
O678	Autres hémorragies pendant l'accouchement	Other intrapartum haemorrhage	Hémorragie
O679	Hémorragie pendant l'accouchement, sans précision	Intrapartum haemorrhage, unspecified	Hémorragie
O720	Hémorragie de la délivrance (troisième période)	Third-stage haemorrhage	Hémorragie
O721	Autres hémorragies immédiates du post-partum	Other immediate postpartum haemorrhage	Hémorragie
O722	Hémorragie du post-partum, tardive et secondaire	Delayed and secondary postpartum haemorrhage	Hémorragie
R040	Épistaxis	Epistaxis	Epistaxis
R041	Hémorragie de la gorge	Haemorrhage from throat	Hémorragie
R042	Hémoptysie	Haemoptysis	Hémoptysie
R048	Hémorragie d'autres parties des voies respiratoires	Haemorrhage from other sites in respiratory passages	Hémorragie
R049	Hémorragie des voies respiratoires, sans précision	Haemorrhage from respiratory passages, unspecified	Hémorragie
R31	Hématurie, sans précision	Unspecified haematuria	Hématurie
R58	Hémorragie, non classée ailleurs	Haemorrhage, not elsewhere classified	Hémorragie
S064	Hémorragie épidurale	Epidural haemorrhage	Hémorragie
S065	Hémorragie sous-durale traumatique	Traumatic subdural haemorrhage	Hémorragie
S066	Hémorragie sous-arachnoïdienne traumatique	Traumatic subarachnoid haemorrhage	Hémorragie
S260	Lésion traumatique du cœur avec hémopéricarde	Injury of heart with haemopericardium	Hémopéricarde
S271	Hémothorax traumatique	Traumatic haemothorax	Hémothorax
T792	Hémorragie traumatique secondaire et récidivante	Traumatic secondary and recurrent haemorrhage	Hémorragie
T810	Hémorragie et hématome compliquant un acte à visée diagnostique et thérapeutique, non classés ailleurs	Haemorrhage and haematoma complicating a procedure, not elsewhere classified	Hémorragie

Unselected Codes:**1. No bleeding**

D473	Thrombocytémie essentielle (hémorragique)	Essential (haemorrhagic) thrombocythaemia	Hémorragique
I694	Séquelles d'accident vasculaire cérébral, non précisé comme étant	Sequelae of stroke, not specified as haemorrhage or infarction	Hémorragique

	hémorragique ou par infarctus		
I859	Varices oesophagiennes, (non hémorragiques)	Oesophageal varices without bleeding	Hémorragique
I982	Varices oesophagiennes non hémorragiques au cours de maladies classées ailleurs	Oesophageal varices without bleeding in diseases classified elsewhere	Hémorragique
2. Chronic disease with bleeding in the definition			
I780	Télangiectasie hémorragique héréditaire	Hereditary haemorrhagic telangiectasia	I780
K518	Autres recto-colites hémorragiques	Other ulcerative colitis	Hémorragique
K519	Recto-colite hémorragique, sans précision	Ulcerative colitis, unspecified	Hémorragique
3. Infectious diseases with bleeding in the definition			
A043	Infection entéro-hémorragique à Escherichia coli	Enterohaemorrhagic Escherichia coli infection	Hémorragique
A270	Leptospirose ictéro-hémorragique	Leptospirosis icterohaemorrhagica	Hémorragique
A91	Fièvre hémorragique due au virus de la dengue	Dengue haemorrhagic fever	Hémorragique
A960	Fièvre hémorragique de Junin	Junin haemorrhagic fever	Hémorragique
A961	Fièvre hémorragique de Machupo	Machupo haemorrhagic fever	Hémorragique
A968	Autres fièvres hémorragiques à arénavirus	Other arenaviral haemorrhagic fevers	Hémorragique
A969	Fièvre hémorragique à arénavirus, sans précision	Arenaviral haemorrhagic fever, unspecified	Hémorragique
A980	Fièvre hémorragique de Crimée [du Congo]	Crimean-Congo haemorrhagic fever	Hémorragique
A981	Fièvre hémorragique d'Omsk	Omsk haemorrhagic fever	Hémorragique
A985	Fièvre hémorragique avec syndrome rénal	Haemorrhagic fever with renal syndrome	Hémorragique
A988	Autres fièvres hémorragiques virales précisées	Other specified viral haemorrhagic fevers	Hémorragique
A99	Fièvre hémorragique virale, sans précision	Unspecified viral haemorrhagic fever	Hémorragique
B303	Conjonctivite hémorragique (aiguë épidémique) (entérovirale)	Acute epidemic haemorrhagic conjunctivitis (enteroviral)	Hémorragique
G361	Leucoencéphalite hémorragique aiguë et subaiguë [Hurst]	Acute and subacute haemorrhagic leukoencephalitis [Hurst]	Hémorragique
4. After effect of cerebral hemorrhage			
I690	Séquelles d'hémorragie sous-arachnoïdienne	Sequelae of subarachnoid haemorrhage	Hémorragie
I691	Séquelles d'hémorragie intracérébrale	Sequelae of intracerebral haemorrhage	Hémorragie
I692	Séquelles d'autres hémorragies intracrâniennes non traumatiques	Sequelae of other nontraumatic intracranial haemorrhage	Hémorragie

5. Accident during surgical and medical care, including other events than a bleeding

T810	Hémorragie et hématome compliquant un acte à visée diagnostique et thérapeutique, non classés ailleurs	Haemorrhage and haematoma complicating a procedure, not elsewhere classified	Hémorragie
Y60	Coupure, piqûre, perforation ou hémorragie accidentelles au d'un intervention chirurgicale ou d'un acte médical	Unintentional cut, puncture, perforation or haemorrhage during surgical and medical care	
Y600	• Au cours d'une intervention chirurgicale	• During surgical operation	Hémorragie
Y601	• Au cours d'une perfusion ou transfusion	• During infusion or transfusion	Hémorragie
Y602	• Au cours d'une dialyse rénale ou autre perfusion	• During kidney dialysis or other perfusion	Hémorragie
Y603	• Au cours d'une injection ou vaccination	• During injection or immunization	Hémorragie
Y604	• Au cours d'une endoscopie	• During endoscopic examination	Hémorragie
Y605	• Au cours d'un cathétérisme cardiaque	• During heart catheterization	Hémorragie
Y606	• Au cours d'une aspiration, d'une ponction et d'un autre cathétérisme	• During aspiration, puncture and other catheterization	Hémorragie
Y607	• Au cours de l'administration d'un lavement	• During administration of enema	Hémorragie
Y608	• Au cours d'autres actes médicaux et chirurgicaux	• During other surgical and medical care	Hémorragie
Y609	• Au cours d'un acte médical et chirurgical, sans précision	• During unspecified surgical and medical care	Hémorragie

6. ICD code for bleeding during abortion or delivery

O031	Avortement spontané incomplet, compliqué d'une hémorragie retardée ou sévère	Spontaneous abortion: Incomplete, complicated by delayed or excessive haemorrhage	Hémorragie
O036	Avortement spontané complet ou sans précision, compliqué d'une hémorragie retardée ou sévère	Spontaneous abortion: Complete or unspecified, complicated by delayed or excessive haemorrhage	Hémorragie
O041	Avortement médical incomplet, compliqué d'une hémorragie retardée ou sévère	Medical abortion: Incomplete, complicated by delayed or excessive haemorrhage	Hémorragie
O046	Avortement médical complet ou sans précision, compliqué d'une hémorragie retardée ou sévère	Medical abortion: Complete or unspecified, complicated by delayed or excessive haemorrhage	Hémorragie
O051	Autres formes d'avortement incomplet, compliqué d'une hémorragie retardée ou sévère	Other abortion: Incomplete, complicated by delayed or excessive haemorrhage	Hémorragie
O056	Autres formes d'avortement complet ou sans précision, compliqué d'une hémorragie retardée ou sévère	Other abortion: Complete or unspecified, complicated by delayed or excessive haemorrhage	Hémorragie
O061	Avortement sans précision, incomplet, compliqué d'une hémorragie retardée ou sévère	Unspecified abortion: Incomplete, complicated by delayed or excessive haemorrhage	Hémorragie
O066	Avortement sans précision, complet ou sans précision, compliqué d'une hémorragie retardée ou sévère	Unspecified abortion: Complete or unspecified, complicated by delayed or excessive haemorrhage	Hémorragie
O071	Échec d'une tentative d'avortement médical, compliqué d'une hémorragie retardée ou sévère	Failed medical abortion, complicated by delayed or excessive haemorrhage	Hémorragie
O076	Échec d'une tentative d'avortement, autres et sans précision, compliqués d'une hémorragie retardée ou sévère	Other and unspecified failed attempted abortion, complicated by delayed or excessive haemorrhage	Hémorragie
O081	Hémorragie retardée ou sévère consécutive à un avortement, une grossesse extra-utérine et molaire	Delayed or excessive haemorrhage following abortion and ectopic and molar pregnancy	Hémorragie

O208	Autres hémorragies du début de la grossesse	Other haemorrhage in early pregnancy	Hémorragie
O209	Hémorragie du début de la grossesse, sans précision	Haemorrhage in early pregnancy, unspecified	Hémorragie
O441	Placenta praevia avec hémorragie	Placenta praevia with haemorrhage	Hémorragie
O460	Hémorragie précédant l'accouchement avec anomalie de la coagulation	Antepartum haemorrhage with coagulation defect	Hémorragie
O468	Autres hémorragies précédant l'accouchement	Other antepartum haemorrhage	Hémorragie
O469	Hémorragie précédant l'accouchement, sans précision	Antepartum haemorrhage, unspecified	Hémorragie
O670	Hémorragie pendant l'accouchement avec anomalie de la coagulation	Intrapartum haemorrhage with coagulation defect	Hémorragie
O678	Autres hémorragies pendant l'accouchement	Other intrapartum haemorrhage	Hémorragie
O679	Hémorragie pendant l'accouchement, sans précision	Intrapartum haemorrhage, unspecified	Hémorragie
O720	Hémorragie de la délivrance (troisième période)	Third-stage haemorrhage	Hémorragie
O721	Autres hémorragies immédiates du post-partum	Other immediate postpartum haemorrhage	Hémorragie
O722	Hémorragie du post-partum, tardive et secondaire	Delayed and secondary postpartum haemorrhage	Hémorragie

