9.3.4. Outcomes

The primary outcomes are:

- **Stroke and systemic embolism (SE)** will be defined as a hospitalisation with one of the two following primary diagnoses:
 - ✓ Ischemic or undefined stroke (Giroud 2015),
 - ✓ Other systemic arterial embolism or surgical procedure for systemic arterial embolism.
- **Major bleeding**, based on International Society on Thrombosis and Haemostasis definition (Schulman 2005) and modified* to take into account the availability of information in the database, will be defined as a hospitalisation with one of the three following primary diagnoses:
 - ✓ Haemorrhagic stroke,
 - ✓ Other critical organ or site bleeding (intrapinal, intraocular, retroperitoneal, intraarticular or pericardial, or intramuscular),
 - ✓ Other bleeding with a transfusion during hospital stay, or resulting in death,

* Causes of death and haemoglobin result are not available to take into account not hospitalized fatal bleeding and bleeding causing a fall in haemoglobin level of 20g/l.
- **Clinically relevant bleeding (CRB)** will be defined as a hospitalisation with one of the five following primary diagnoses:
 - ✓ Haemorrhagic stroke,
 - ✓ Other critical organ or site bleeding (intrapinal, intraocular, retroperitoneal, intraarticular or pericardial, or intramuscular),
 - ✓ Gastro-intestinal bleeding,
 - ✓ Urogenital bleeding,
 - ✓ Other bleeding (ICD-10 codes in annex 1).
- **Death** defined as all-cause death (cause of death not available in the database).
- **Acute coronary syndrome (ACS)** will be defined as a hospitalisation with one of the two following primary diagnoses (Bezin 2015):
 - ✓ Myocardial infarction (MI),
 - ✓ Unstable angina.

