9.3.6. Healthcare resources

Healthcare resources use will be described from reimbursed claims and hospitalisation information, and classified as:

- Cardiovascular hospitalisations defined as all hospitalisations with cardiovascular primary diagnosis or diagnosis-related group of cardiovascular disease,
- Non-cardiovascular hospitalisations defined as all hospitalisations other than those defined above,
- Medical visits and technical acts,
- Cardiovascular and antidiabetic drugs reimbursed,
- Non-cardiovascular/antidiabetic drugs reimbursed,
- Lab tests,
- Products and services,
- Nursing acts,
- Physiotherapy acts,
- Transports,
- Sick leave daily allowances, disability allowances, pension,
- Other medical resources.

Healthcare resources related to AF will be:

- Specific Hospitalisations: Hospitalisations with primary diagnosis of AF, or cardioversion, or catheter ablation procedure, or stroke or systemic embolism, or CRB,
- Specific drugs: DOAC, VKA, beta-blockers, amiodarone, dronedarone, other antiarrhythmics,
- Specific lab tests: INR, haemostasis tests, creatinine, creatinine clearance, ALAT, ASAT, including sampling,
- Specific medical visits: cardiologist visit, other medical visits with date corresponding to the date of prescription of specific drugs or lab tests, neurologist visit after stroke event,
- Specific transport: Transport with date corresponding to the date of a specific hospitalisation, medical visit, medical procedure, or lab test.

Healthcare resources cost will be estimated using the French HAS methodological guide for economic evaluations (2011):

- From a societal perspective using diagnosis-related group (DRG) cost for hospitalisations and total cost for other healthcare resources.
- From the French healthcare insurance perspective using stay-related group (STG) cost for hospitalisations and reimbursed cost for other healthcare resources.

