9.5. STUDY SIZE

The Bordeaux Pharmacoépi (BPE) has performed a previous VKA study in the EGB database, a 1/97 permanent random sample of the SNIIRAM, using similar definitions used in this protocol (Blin 2015). Between 2007 and 2011, the numbers of subjects who initiated a VKA for SPAF were 2 197 for the specific NVAF population and 3 345 for the sensitive NVAF population, which represent about 50 000 and 75 000 subjects respectively in the SNIIRAM each year, and 100 000 and 150 000 respectively for a two-year inclusion period.

Among them, the number of subjects treated with rivaroxaban, dabigatran, and VKA, as well as the number of subjects who can be matched for each comparison (rivaroxaban versus VKA, rivaroxaban versus dabigatran) will be a result of the study. Anyway, it should be clearly higher than the 7 131 and 7 133 subjects randomized in the rivaroxaban and VKA arms of the ROCKET AF trial (Patel 2011).

In the previous VKA study cited above (Blin 2015), the outcome incidence rate during VKA exposure was estimated in the specific NVAF population (with similar results for the sensitive NVAF population):

- Stroke and systemic arterial embolism: 1.6 per 100 person-years (PY), 95%CI [1.1-2.1],
- ACS: 1.6 per 100 PY, 95%CI [1.0-2.1],
- CRB: 2.6 per 100 PY, 95%CI [1.9-3.3], with 0.5 [0.3-0.9] cerebral bleeding hospitalisation, 0.8 [0.4-1.1] digestive bleeding hospitalisation, and 1.3 [0.9-1.8] other bleeding hospitalisation,
- Death: 3.5 per 100 PY, 95%CI [2.7-4.3].

Within the ranges of incidence rates of ROCKET AF trial outcomes, the following table shows the minimum hazard ratio that can be identified with a 95% confidence interval excluding 1, for the study group compared to a reference group, according to the incidence of an outcome in the reference group and the sample size for each group for analysis of matched subjects (1:1).

Minimum hazard ratio (< 1 and > 1) with a 95% confidence interval excluding 1, for the study group compared to a reference group, according to the incidence of an outcome in the reference group, sample size for each group (1:1 matching) and normal distribution

Incidence in the reference group	Hazard ratio	Sample size			
		5 000	10 000	15 000	20 000
0.5%	< 1 / >1	0.24 / 2.19	0.43 / 1.78	0.58 / 1.52	0.65 / 1.42
1.0%	< 1 / >1	0.43 / 1.78	0.58 / 1.52	0.70 / 1.35	0.75 / 1.28
1.5%	< 1 / >1	0.53 / 1.61	0.66 / 1.41	0.75 / 1.28	0.79 / 1.23
2.0%	< 1 / >1	0.59 / 1.52	0.70 / 1.35	0.78 / 1.24	0.82 / 1.20

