- **Outcomes:** Since deaths are recorded in the database using the national death registry, there is no information bias for this outcome. Death is a competing risk of other clinical outcomes (stroke and SE, ACS, CRB). To take into account this, the model proposed by Fine and Gray will be used to analyse clinical outcomes (Fine 1999). Clinical outcomes will be defined using the ICD-10 discharge primary diagnosis. Miscoding cannot be excluded but should be sparse for the clearly defined events studied. Nevertheless, the PMSI coding is fully independent from the study and there is no reason that a potential miscoding will be different between anticoagulant drugs, excluding an information bias. For strokes classified as undefined because CT scan or NMR were not performed, it was decided to classify undefined stroke with ischemic stroke but some could be cases of haemorrhagic stroke. A sensitivity analysis will be performed by classifying undefined stroke as haemorrhagic stroke.

Counfounding bias

The choice between a VKA and a DOAC could be related to potential confounding. To control this potential bias, the main analysis will use 1:1 matching on high dimensional propensity score (hdPS), which includes main known risk factors (gender, age, AF risk factor score, bleeding risk factor score). Indeed, one of the main limits of this database, as for many administrative databases, is the lack of information for some risk factors (e.g. smoking status, body mass index, biological results, etc.), which may or not be confounders. Without such information, it is not possible to compare the distribution of these risks factors between treatment groups, or to take it into account in the matching.

The propensity score is a statistical technique that attempts to estimate the effect of a treatment, policy, or other intervention by accounting for the covariates that predict receiving the treatment. The propensity score, and more recently hdPS (Schneeweiss 2009, Rassen 2012), were developed to summarise a large set of variables that characterize each subject for status and unmeasured confounders not recorded in a database (i.e. drugs, medical status, hospitalisation, other co-morbidities directly, or indirectly linked with unmeasured confounders). Adjusting for large numbers of covariates ascertained from subject healthcare claims data may improve control of confounding, as these variables may collectively be proxies for unobserved factors.

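### Annex 1 lets D683, a code labelled by the anticoagulant exposure and naming no bleed, count alone as CRB, and 9.9 rules out information bias without considering it

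*Protocol*

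**What the plan says.** Annex 1 builds the bleeding code list by key word and then prunes it: "ICD label that do not correspond to a bleeding event were excluded (grey list"). D683, "Haemorrhagic disorder due to circulating anticoagulants", is among the selected codes and does not appear in the list of unselected ones.

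Section 9.3.4 says that CRB "will be defined as a hospitalisation with one of the five following primary diagnoses". The fifth is "Other bleeding (ICD-10 codes in annex 1"). No second code, transfusion or bleeding site is required. Major bleeding is stricter in its third component: "Other bleeding with a transfusion during hospital stay, or resulting in death".

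On outcome coding, section 9.9 accepts that some miscoding may occur but concludes that "there is no reason that a potential miscoding will be different between anticoagulant drugs, excluding an information bias".

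The status of CRB is not uniform. Section 9.3.4 lists it under the primary outcomes; section 8 places its comparison among the secondary objectives.

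**The concern.** Most selected labels in Annex 1 name a bleed or the place where it happened. D683 names a disorder and attributes it to anticoagulants, the exposure that defines the cohort. A stay with D683 as its only bleeding code therefore becomes a CRB event with nothing else in the stay to confirm a bleed.

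That matters for a comparison between anticoagulants if the code is used differently for VKA and DOAC patients. One plausible route is laboratory detection of an excessive anticoagulant effect. Section 9.3.3 notes that VKA dosage varies between subjects and over time, and section 9.3.6 counts "Specific lab tests: INR, haemostasis tests" among the AF-related resources. If stays without a bleed were coded D683 more often under VKA, rivaroxaban would look safer on CRB than it is. That would also favour the hypothesis stated in the ENCePP checklist (comment 2.1.5), that DOACs do better than VKA. Matching on the hdPS does not remove such an error, because it lies in how the outcome is classified and not in who receives which drug.

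The categorical statement in 9.9 leaves no room for this. The planned sensitivity analyses in 9.7.1 (Generalities) concern grace periods, the NVAF definition and the reclassification of unspecified events as haemorrhagic stroke; none touches D683.

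**Working it through.** **Step 1: the plan's own rate.** Section 9.5 gives, for the earlier VKA study, "CRB: 2.6 per 100 PY, 95%CI [1.9-3.3"]. Its parts are 0.5 cerebral, 0.8 digestive and 1.3 other bleeding per 100 PY. 0.5 + 0.8 + 1.3 = 2.6, so the stated total is reproduced. D683 would fall in the other-bleeding part.

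**Step 2: what is not in the protocol.** Two quantities are needed and neither is given, so both are assumed:
- n = rate of D683 stays without a bleed under VKA, taken as 0.1, 0.2 or 0.3 per 100 PY. As a share of other bleeding, 0.1/1.3 = 8% and 0.3/1.3 = 23%.
- r = ratio of that rate on rivaroxaban to that on VKA, taken as 0, 0.5, 1 or 2.

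**Step 3: apparent CRB ratio when the true ratio is 1.**

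Apparent ratio = (2.6 − n + r·n) / 2.6

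| n per 100 PY | r = 0 | r = 0.5 | r = 1 | r = 2 |
|---|---|---|---|---|
| 0.1 | 0.96 | 0.98 | 1.00 | 1.04 |
| 0.2 | 0.92 | 0.96 | 1.00 | 1.08 |
| 0.3 | 0.88 | 0.94 | 1.00 | 1.12 |

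For example, n = 0.3 and r = 0 gives 2.3/2.6 = 0.885. Equal rates leave a true null at 1.00, and a higher rate on rivaroxaban reverses the direction.

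**Step 4: precision at the largest assumed value.** Take 20 000 person-years per arm (20 000 matched subjects with one year each, an assumption), n = 0.3 and r = 0.
- Events: VKA 20 000 × 2.6/100 = 520; rivaroxaban 20 000 × 2.3/100 = 460.
- SE of the log ratio = √(1/520 + 1/460) = 0.0640.
- 95% CI = 0.885 × exp(±1.96 × 0.0640) = 0.780 to 1.003.

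The interval just includes 1. This treats event counts as Poisson and ignores matching and the competing risk of death.

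**Step 5: the plan's own yardstick.** The table in section 9.5 shows 0.84 for 2.5% incidence and 20 000 per group. A spurious ratio of 0.84 with r = 0 would need n = 0.16 × 2.6 = 0.42 per 100 PY, about a third of other bleeding (0.42/1.3 = 32%).

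**The case against.** The strongest reply is that nothing in the protocol shows D683 being used without a bleed. The printed label says haemorrhagic, the list is headed as codes for bleeding leading to hospitalisation, and it had already passed a step meant to remove labels that are not bleeding events. Every compared group takes an anticoagulant, so the label alone does not separate the arms. Section 9.3.6 lists INR as a resource without assigning it to VKA and says nothing about admissions. All of this stands, and it limits the claim to a possibility.

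Two further points also stand. The main objective uses major bleeding, where other bleeding already needs transfusion or death, so D683 alone cannot reach it. And requiring supporting evidence in the main CRB definition would drop true bleeds coded only as D683, with an unknown balance between drugs.

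Two replies carry less weight. Section 9.7.1 (Outcomes) reports incidence by individual diagnosis, but that shows other bleeding as a group and does not isolate D683. Decision rules may be left to an SAP, but the code list and the statement in 9.9 are fixed in the protocol itself.

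A reader might infer that stays without a bleed do enter CRB at a rate that depends on the drug, or that 0.3 per 100 PY would by itself produce a significant false benefit. The documents support neither. The first needs coding frequencies that are not given. The second fails on its own assumptions, since 460 against 520 events gives an interval reaching 1.003. More person-years would narrow that interval, but the number of matched subjects is left as a result of the study.

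**Conclusion.** The point holds as a gap in the outcome definition and an overstatement in 9.9, not as a demonstrated bias. D683 is sufficient alone for CRB, its label names the exposure and no bleed, and 9.9 dismisses information bias without addressing it.

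In the illustration, 0.1 to 0.3 per 100 PY of non-bleed D683 stays confined to VKA moves a true ratio of 1 to between 0.96 and 0.88. Those rates and the zero on rivaroxaban are assumptions. With equal rates there is no bias from a true null, and the direction could be the opposite.

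The stakes are those of a secondary objective under section 8, despite the placement of CRB in 9.3.4. Codes D698 and D699 are also unspecific, but their labels do not name anticoagulants, so the exposure argument does not extend to them.

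**What to change.** Keep the main CRB definition as it is and make three changes:

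- In 9.7.1 (Generalities), add a pre-specified sensitivity analysis of CRB. In it, a stay with primary diagnosis D683 counts only if the same stay also has another Annex 1 bleeding code, a transfusion or in-hospital death. Associated diagnoses then serve only to corroborate an event, which respects the caution in section 9.4 against defining outcomes by them.
- Tabulate, by drug, the D683 stays with and without such support.
- Amend 9.9 to say that differential coding of this exposure-labelled code cannot be excluded and is examined in that analysis.

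The cost is one extra analysis and one small table, from data already planned for extraction. Some true bleeds coded only as D683 will drop out of the sensitivity analysis; the table shows how many unsupported stays there are for each drug, and the main analysis retains them.
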